3.7 Data Monitoring Committee

No Data Monitoring Committee will be convened for this study.

3.8 Premature Withdrawal from Study

Subjects may withdraw at any time, or be dropped from the study at the discretion of the investigator should any untoward effects occur and/or for safety reasons. In addition, a subject may be withdrawn by the investigator or the Sponsor if he/she violates the study plan or for administrative reasons. The investigator or study coordinator must notify the Sponsor immediately when a subject has been withdrawn due to an adverse event.

The circumstances above are referred to as premature withdrawal from the study, and the reason for premature withdrawal should be clearly documented and detailed in the source documentation. The investigator should make every attempt to evaluate the subject's safety, including resolution of ongoing AEs, at the time of premature withdrawal. If a subject wants to withdraw from the study before all doses are administered or prior to the last planned study visit, the subject will be asked to be followed for safety for the duration of the study. When a subject withdraws, or is withdrawn, from the study, the procedures described in section 5.5.1, Early Termination Visit should be completed if possible.

The reasons for premature withdrawal from the study include: Adverse event, death, withdrawal of consent, lost to follow-up, administrative reason, and protocol deviation. These reasons are described in greater detail below.

3.8.1 Adverse Event

For any subject withdrawn from study participation prior to the planned Study Termination Visit, it is important to determine if an AE was associated with the reason for discontinuing the study. This AE must be identified on the AE eCRF page by indicating "Withdrawn from study due to AE". Any ongoing AEs at the time of study withdrawal must be followed until resolution or stabilization.

Subjects who develop a serious adverse event (SAE) judged to be possibly or probably related to the study vaccine, including hypersensitivity reactions, should not receive subsequent vaccination.

3.8.2 **Death**

For any subject withdrawn from study participation due to death, this should be noted on the Study Termination eCRF page and the associated SAE that led to the death must be reported.

3.8.3 Withdrawal of consent

The subject or parent(s)/legal guardian(s) can withdraw consent for participation in the study at any time without penalty or loss of benefit to which the subject is otherwise entitled. Reason for early termination should be deemed as "withdrawal of consent" if the subject withdraws from participation due to a non-medical reason (i.e., reason other than AE). If the subject or parent(s)/legal guardian(s) intends to withdraw consent from the study, the investigator should clarify if the subject will withdraw completely from the study or if the subject will continue study participation for safety, or a subset of other study procedures. If the subject requests complete withdrawal from the study, no further study interventions will be performed with the subject.

3.8.4 Lost to Follow-Up

For subjects who fail to show up for final visits (clinic or telephone contacts), or for three consecutive visits, study staff are encouraged to make at least three documented attempts to contact the subject by telephone and at least one documented written attempt to contact the subject or parent(s)/legal guardian(s) to encourage the completion of study termination procedures. These efforts to contact the subject should be recorded in the source document. The termination date for the subject to be captured on the Study Termination eCRF page is the date of the last successful contact (clinic visit or telephone) with the subject.

3.8.5 Administrative Reason

Examples for subjects withdrawn from the study due to administrative reason can include: Sponsor decision to terminate the study, subject meeting a pre-specified withdrawal criterion, subject discontinuation for insurance issues, moving, no time, etc. This reason should be noted in the Study Termination eCRF page and any ongoing AEs at the time of study withdrawal must be followed until resolution/stabilization.

If the clinical study is prematurely terminated by the Sponsor, the investigator is to promptly inform the study subjects and local EC/IRB and should assure appropriate therapy and follow up for the subjects. All procedures and requirements pertaining to the archiving of study documents should be followed. All other study materials (study medication/vaccines, etc.) must be returned to the Sponsor.

For subjects who are withdrawn from the study due to receipt of an excluded medication/vaccination or due to significant protocol non-compliance, this reason should be noted in the Study Termination eCRF page.

Subject Compliance: Subjects should submit diary data each day for the first 7 days after each vaccination. Subject must be contacted by phone if they fail to submit data on 2 or more days during the first 7 days after each vaccination.

3.8.6 Protocol Deviation

A protocol deviation is any change, divergence, or departure from the study design or procedures of a study protocol. In general, subjects associated with protocol deviations may remain in the study unless continuation in the study jeopardizes the subject's health, safety, or rights.

Investigators will apply due diligence to avoid protocol deviations. Under no circumstances should the investigator contact GSK or its agents, if any, monitoring the study to request approval of a protocol deviation, as no authorized deviations are permitted. If the investigator feels a change to the protocol would improve the conduct of the study this must be considered a protocol amendment, and unless such an amendment is agreed upon by GSK and approved by the IRB/EC and health authorities it cannot be implemented.

Any subject who becomes pregnant during the study, despite the protocol requirement for adequate contraception, will not receive further vaccination (s) but should be encouraged to continue participating in the study for safety follow-up. The site must complete a Pregnancy Report eCRF (initial report) as soon as possible after learning of pregnancy occurrence (see section 7.1.6, Pregnancies for further details). If the subject withdraws from the study for any of the above categories except death, the site will obtain permission from the subject to continue to remain in contact with her until the outcome of the pregnancy is known, even if the outcome is not known until after the subject reaches the end of follow-up period.

3.9 End of Study

Most clinical trials intended to support the efficacy/immunogenicity and safety of an Investigational Product proceed to full completion of planned sample size accrual.

A subject is considered to have completed the study when he/she has completed the last study visit/contact (Follow on subjects at Day 181 and the naive subjects at **D**ay 241) and provided safety information.

For the purpose of this protocol, the end of study is defined as the date of the last testing/reading released of human biological samples or imaging data, related to primary and secondary end points, to be achieved no later than 8 months after Last Subject Last Visit (LSLV).

(Amended 4 April 2018)

4. SELECTION OF STUDY POPULATION

4.1 Inclusion Criteria

Follow-on Participants

- Subjects from Finland and Poland previously enrolled in study V102_15 who have received all planned meningococcal vaccinations in the study¹
- Who have not received any additional meningococcal vaccination since the last meningococcal vaccination administered in the parent trial.
- Who have given written informed consent or assent (as applicable) after the nature of the study has been explained according to local regulatory requirements, prior to study entry. If the subject is under age 18 at the time of enrollment, the parent(s)/ legal guardian(s) of the subject should have given their written consent.
- Individuals of who the investigator believes can and will comply with the requirements of the protocol (e.g. use of an eDiary, return for follow-up visits, available for phone contacts).
- Individuals in good health as determined by the outcome of medical history, physical examination and clinical judgment of the investigator.

Naive Group

• Male and female individuals of similar age (approximately 12-20 years) to follow-on subjects from V102_15 trial.

- Who have not received any meningococcal vaccination since birth
- Individuals who have given their written informed consent or assent (as applicable) after the nature of the study has been explained according to local regulatory requirements, prior to study entry. If the subject is under age 18 at the time of enrollment, the parent(s)/ legal guardian(s) of the subject should have given their written consent.
- Individuals of who the investigator believes can and will comply with the requirements of the protocol (e.g. use of an eDiary, return for follow-up visits, available for phone contacts).

_

¹ Subjects will be eligible if they have received meningococcal vaccinations according to randomization assignment, irrespective of protocol-specified window.

• Individuals in good health as determined by the outcome of medical history, physical examination and clinical judgment of the investigator.

4.2 Exclusion Criteria

Follow-on Participants:

Follow-on individuals not eligible to be enrolled in the study are those with:

- History of any meningococcal vaccine administration since last meningococcal vaccination administered in V102 15 parent study.
- Current or previous, confirmed or suspected disease caused by *N. meningitidis*, since termination from parent study.
- Household contact with and/or intimate exposure to an individual with any laboratory confirmed *N. meningitidis* infection within 60 days of enrollment.
- If the subject is female of childbearing potential, sexually active, and has not used any of the acceptable contraceptive methods¹ for at least 2 months prior to study entry and for the duration of the trial.
- Pregnancy or breast-feeding .
- History of severe allergic reactions after previous vaccinations or hypersensitivity to any vaccine component including diphtheria toxoid (CRM197) and latex.
- Progressive, unstable or uncontrolled clinical conditions.
- Any confirmed or suspected condition with impaired/altered function of immune system (immunodeficient or autoimmune conditions).
- Chronic administration (defined as more than 14 days) of immunosuppressants or other immune-modifying drugs within three months prior to the study vaccination or planned use throughout the study period. (For corticosteroids, this means prednisone, or equivalent, ≥ 20 mg/day. Inhaled, intranasal and topical steroids are allowed).

- Abstinence

Hormonal contraceptive (such as oral, injection, transdermal patch, implant) if used for at least 30 days prior to informed consent

- Diaphragm preferably with spermicide, tubal occlusion device

- Intrauterine device (IUD)

- Tubal ligation

- Male partner using condom preferably with spermicide

- Male partner having been vasectomized at least six months prior to informed consent

¹ The following birth control methods are considered effective:

- Administration of blood, blood products and/or plasma derivatives or any parenteral immunoglobulin preparation in the 3 months prior to study enrolment.
- Received an investigational or non-registered medicinal product within 30 days prior to informed consent.
- Administration of any vaccine within 14 days (for inactivated vaccines) or 28 days (for live vaccines) prior to enrollment in the study, or within 7 days after vaccination in the study. (See section 4.3 for additional details).
- Clinical conditions representing a contraindication to intramuscular vaccination and/or blood draws.
- Who have received systemic antibiotic treatment within 3 days prior to any blood draw.
- Any other clinical condition that, in the opinion of the investigator, might pose additional risk to the subject due to participation in the study.

Naive Individuals

Naive individuals not eligible to be enrolled in the study are those with:

- History of any meningococcal vaccine administration since birth.
- Current or previous, confirmed or suspected disease caused by *N. meningitidis*.
- Household contact with and/or intimate exposure to an individual with any laboratory confirmed *N. meningitidis* infection within 60 days of enrollment.
- If the subject is female of childbearing potential, sexually active, and has not used any of the acceptable contraceptive methods¹ for at least 2 months prior to study entry and for the duration of the trial
- Pregnancy or breast-feeding.

- Abstinence

- Hormonal contraceptive (such as oral, injection, transdermal patch, implant) if used for at least 30 days prior to informed consent

- Diaphragm preferably with spermicide, tubal occlusion device
- Intrauterine device (IUD)
- Tubal ligation

- Male partner using condom preferably with spermicide

- Male partner having been vasectomized at least six months prior to informed consent

¹ The following birth control methods are considered effective:

- History of severe allergic reactions after previous vaccinations or hypersensitivity to any vaccine component including diphtheria toxoid (CRM197) and latex.
- Progressive, unstable or uncontrolled clinical conditions.
- Any confirmed or suspected condition with impaired/altered function of immune system (immunodeficient or autoimmune conditions).
- Chronic administration (defined as more than 5 days) of immunosuppressants or other immune-modifying drugs within 30 days prior to the study enrolment. (For corticosteroids, this means prednisone, or equivalent, ≥ 20 mg/kg/day. Inhaled, intranasal and topical steroids are allowed).
- Administration of blood, blood products and/or plasma derivatives or any parenteral immunoglobulin preparation in the past 3 months or planned use throughout the study period.
- Received an investigational or non-registered medicinal product within 30 days prior to informed consent.
- Individuals who are part of study personnel or close family members conducting this study.
- Administration of any vaccine within 14 days (for inactivated vaccines) or 28 days (for live vaccines) prior to enrollment in the study, or within 7 days after first vaccination, and/or planned use of any vaccine 7 days prior to and 7 days after second vaccination. (See section 4.3 for additional details)
- Clinical conditions representing a contraindication to intramuscular vaccination and/or blood draws.
- Who have received systemic antibiotic treatment within 3 days prior to any blood draw.
 - Any other clinical condition that, in the opinion of the investigator, might pose additional risk to the subject due to participation in the study.

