On Day 1, subjects will be enrolled after screening for eligibility and having their medical history evaluated (since birth for naive subjects and since end of study V102_15 for follow-on subjects). All subjects will have approximately 20 mL of blood drawn after enrolment and vaccinated as detailed in Tables 2 and 3.

Number of Subjects planned: Up to 852 subjects may be enrolled into this study, including up to 652 follow-on subjects from the parent V102_15 study and 200 vaccinenaive subjects of similar age to the follow-on subjects.

Study Population and Subject Characteristics:

Subjects will be included in the study if in good health as judged by physical examination and medical history and if they meet all specified eligibility criteria.

Inclusion criteria: Adolescents from 12-20 years of age, generally in good health, and available for all study visits, who/whose legally acceptable representative has given written informed consent at the time of enrollment. Female subjects of childbearing potential must have a negative urine pregnancy test.

Exclusion criteria: For all subjects: Serious, acute, or chronic illnesses. Previous or suspected disease caused by *N. meningitidis*. Exposure to individuals with clinically proven meningococcal disease or clinical bacterial meningitis without further microbiologic characterization.

Follow on subjects from V102_15 study: Subjects previously enrolled in study V102_15 in Poland and Finland who have received all planned meningococcal vaccinations in the study and who have not received any additional meningococcal vaccination since the last meningococcal vaccination administered in the parent trial.

Naive subjects: Previous immunization with any meningococcal vaccine.

The complete list of inclusion and exclusion criteria is included in protocol section 4., Selection of Study Population.

Study Procedures:

The study comprises 3 clinic visits (at **D**ays 1, 6 and 31) and 3 safety phone calls (at **D**ays 16, 91 and 181) for follow-on subjects. Naive subjects will have 5 clinic visits (at **D**ays 1, 31, 61, 66 and 91) and 4 safety phone calls (at **D**ays 16, 76, 151 and 241).

Written informed consent and, if applicable, written assent will be obtained before conducting any study-specific procedures.

Blinding: All subjects will receive the vaccine as an open label manner.

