3.5.1 Blood Specimens

A sample of approximately 20 mL sample of blood will be drawn from all follow on subjects at visits Day 1 before vaccination, and at visits Day 6 and **D**ay 31 and from all naive subjects at Visit Day1 before the vaccination and at visits Day 31, Day 66 and Day 91. The blood volume will not exceed 20 mL at each time point. A volume of 20 mL is

required in order to provide the necessary serum volume (approximately half of the blood draw volume) for the planned serology assays.

The blood will be used for immunological assays. See section 7., Assessments for additional details.

The total amount of blood collected over the study period per subject will be approximately 60 mL for follow-on subjects and 80 mL for naive subjects.

In order to minimize pain an anesthetic cream or patch (e.g. EMLA adhesives or cream) may be used at the site of blood sample draw, according to local practice. Not more than two attempts should be made to draw the required volume of blood.

The blood will be processed according to the Clinical Specimen Lab Manual and the serum will be distributed in aliquots using the tubes provided. All the aliquots will be stored at a temperature of -18°C or **below**. Each serum tube will be labeled with the labels provided by GSK. Serum samples will be sent to the sponsor or will be collected by a representative of the sponsor.

Complete instructions for labeling and storage of serum samples are included in the Clinical Specimen Lab Manual, which is stored in the investigator site file.

Testing of samples will be performed at GSK, Clinical Laboratory Sciences, Marburg, Germany or a delegate laboratory.

Samples will be retained in accordance with regulatory guidance for retention of essential study documents as described in section 10.

(Amended 4 April 2018)

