Any treatments and/or medications specifically contraindicated, e.g., any investigational or non-registered product, any immunosuppressants and immune-modifying drugs including systemic steroids, any immunoglobulins and blood products should be checked at each study visit / safety phone call subsequent to the study vaccination. If any became applicable during the study, it will not require withdrawal of the subject from the study but may determine a subject's evaluability in the per-protocol analysis. See section 8.3 for definition of study populations to be evaluated.

Any vaccine not foreseen in the study protocol in the period starting at Visit 1 and ending at Last visit must be recorded in the eCRF.

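### The naive-cohort steroid exclusion in Protocol 4.2 is written per kilogram (≥ 20 mg/kg/day) where the follow-on rule is ≥ 20 mg/day, so it excludes almost nobody; the unit should be corrected

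*Protocol*

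**What the plan says.** Protocol 4.2 has separate exclusion lists for follow-on and naive subjects, and each has one bullet on immunosuppressants.

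- Follow-on: "Chronic administration (defined as more than 14 days) of immunosuppressants or other immune-modifying drugs within three months prior to the study vaccination", or planned use during the study, with the corticosteroid dose set at "prednisone, or equivalent, ≥ 20 mg/day".
- Naive: "Chronic administration (defined as more than 5 days) of immunosuppressants or other immune-modifying drugs within 30 days prior to the study enrolment", with the corticosteroid dose set at "prednisone, or equivalent, ≥ 20 mg/kg/day".

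Both bullets exempt inhaled, nasal and topical steroids. The dose qualifies corticosteroids only; other immunosuppressants stay excluded in both cohorts.

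Protocol 6.5 names systemic steroids twice without a dose: once among prior medications to record if taken in the three months before enrolment, and once among contraindicated products that "should be checked at each study visit / safety phone call subsequent to the study vaccination". SAP 7.7 has deviation codes for forbidden medication (230.x) and unmet entry criteria (200). Both depend on what the protocol forbids or requires, and neither states a dose.

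**The concern.** The same number appears with two different units in two parallel bullets. Read literally, the naive rule applies only at doses far above the follow-on threshold, so a naive subject on a substantial oral steroid course would pass it while a follow-on subject on the same long course would not.

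The naive cohort is the control for the primary comparison of Day 1 antibody levels. It is also the comparator for the Day 31 responses in secondary immunogenicity objectives 1 and 3, where response to vaccination is what an immunosuppressant exclusion is meant to protect. Sites cannot repair the figure themselves: Protocol 3.8.6 rules out sponsor-approved deviations and sends any change through an amendment. The text as written therefore governs entry.

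**Working it through.** There is no sample-size or power figure to reproduce here. The check is unit arithmetic followed by a search for any correcting text.

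**Inputs**

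- Naive threshold: 20 mg/kg/day (Protocol 4.2, Naive Individuals).
- Follow-on threshold: 20 mg/day (Protocol 4.2, Follow-on Participants).
- Age: about 12 to 20 years (Protocol 4.1).
- Body weight *w*: not given in the documents; assumed 30 to 100 kg.

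**Formulas**

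- Naive daily dose threshold = 20 × *w* mg/day.
- Ratio to follow-on threshold = (20 × *w*) / 20 = *w*, with *w* in kg.

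| Assumed weight | Naive threshold | Follow-on threshold | Ratio |
|---|---|---|---|
| 30 kg | 600 mg/day | 20 mg/day | 30 |
| 50 kg | 1000 mg/day | 20 mg/day | 50 |
| 80 kg | 1600 mg/day | 20 mg/day | 80 |
| 100 kg | 2000 mg/day | 20 mg/day | 100 |

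The two rules would agree only at *w* = 1 kg. A naive subject taking 20 to 599 mg/day is not caught by the steroid clause at any weight in the range. The conclusion does not depend on which end of the range is right.

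**The two bullets side by side**

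| Element | Follow-on | Naive | Stricter |
|---|---|---|---|
| Duration | more than 14 days | more than 5 days | Naive |
| Look-back | three months | 30 days | Follow-on |
| Planned use in study | covered | not covered | Follow-on |
| Steroid dose | 20 mg/day | 20 mg/kg/day | Follow-on, by a factor of 30 to 100 |

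**Search for a correction**

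- The Synopsis exclusion summary does not mention steroids. It gives "For all subjects: Serious, acute, or chronic illnesses" and refers to section 4 for the full list.
- Protocol 4.1 and 4.3 give no steroid dose.
- Protocol 6.5 names systemic steroids without a dose. Its check on contraindicated products applies after vaccination, whereas the first blood sample is taken from "all naive subjects at Visit Day1 before the vaccination".
- The SAP gives no steroid dose.
- The changes listed in Appendix A do not touch this criterion.

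So no other text restates or overrides the naive figure.

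**The case against.** The strongest reply is that other provisions already do most of the work. Protocol 4.1 requires "Individuals in good health as determined by the outcome of medical history, physical examination and clinical judgment of the investigator", and the naive list separately excludes impaired or autoimmune conditions and unstable disease. Protocol 6.5 describes its prior-medication list as drawn from the entry criteria and includes systemic steroids with no dose floor. SAP code 230.101 can remove a subject with forbidden medication at Day 1 from the Per Protocol Set for persistence, so the cover reaches the pre-vaccination sample and is not limited to later visits.

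This stands as partial cover. Many adolescents on high-dose steroids would be stopped by the health criteria. However, those criteria rest on diagnosis and judgement, and a course for a resolved or stable non-autoimmune condition need not trigger them. Section 6.5 does not alter eligibility. Code 230.101 acts on the Per Protocol Set only, while Protocol 8.4.2.2.2 makes the Full Analysis Set primary.

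A second reply is that the intended unit is not proven. The bullets differ in three other respects, so one may not have been copied from the other, and a weight-based rule with a wrong number is possible. That is fair, and it is why the sponsor should confirm the unit. The parallel follow-on rule still makes mg/day the best-supported reading.

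A reader might also infer that the naive cohort is screened more loosely throughout. The documents do not support that: the 5-day duration rule is stricter than the follow-on rule, and non-steroid immunosuppressants remain excluded.

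**Conclusion.** The naive steroid threshold is wrong as an operative figure and should be corrected. Its size is a dose ratio of 30 to 100, resting on an assumed body weight of 30 to 100 kg. That mg/day was intended is an inference from the parallel criterion.

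A reader might go further and infer that the naive control data, and so the persistence comparison, are biased. The documents do not support that. They give no steroid prevalence and nothing from which to derive a direction of effect. With the health criteria in place, few affected subjects are to be expected, so the likely effect is small; that is a judgement, and the documents do not allow it to be quantified. The primary objective has no hypothesis and no success criterion (Protocol 8.2.1.2 and 8.4.2.2.1), so no pass/fail conclusion can change.

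The differences in duration, look-back and planned use may be deliberate. They are a question for the sponsor and not part of the error.

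**What to change.** 1. In the Naive Individuals list of Protocol 4.2, change the corticosteroid threshold from ≥ 20 mg/kg/day to ≥ 20 mg/day, with the sponsor confirming the unit. Make the change in the next amendment.
2. Keep the more-than-5-days naive duration rule. In the same query, ask whether the differences in duration, look-back and planned use are intended, and do not harmonise them by default.
3. If enrolment has occurred, list recorded systemic steroid use in both cohorts from the section 6.5 records, for information or a sensitivity analysis. Section 6.5 does not mention dose, so dose may not be available for every subject.
4. Do not add a retrospective Per Protocol exclusion for naive subjects alone. They met the criterion in force, so code 200 would not fit, and the exclusion would be one-sided in an open-label study. It would also leave the Full Analysis Set unchanged; only correction before enrolment affects that set.

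The cost is one unit, one query and, if needed, one listing. Because the change affects who is eligible, it needs the approvals in Protocol 13.4; combining it with the next amendment avoids a separate round.
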